### **5.12. Physical Activity History**

In 2008, *Physical Activity (PA) Guidelines for Americans*, published by the US Department of Health and Human Services, recommended that all adults should strive to engage in a minimum of 150 minutes per week of moderate- to vigorous-intensity physical activity. This recommendation was based on a large body of epidemiological and exercise training studies that showed that physical activity was associated with reduced risk of premature death, CHD, stroke, hypertension, hyperlipidemia, type 2 DM, metabolic syndrome, depression, cognitive function (older adults), and improved cardiorespiratory and muscular fitness. Since the publication of those recommendations, there has been increasing evidence that prolonged sedentary behavior is associated with increased risk of CVD mortality, obesity, cardiometabolic risk factors, and type 2 DM independent of physical activity.

Physical activity is a complex behavior that can occur in several domains and contexts, including occupation, domestic or self-care, transportation, and discretionary or leisure-time. Physical activity can be further characterized in terms of the frequency and duration across a range of intensity levels, ranging from light to vigorous. The consequences of maintaining a physically active lifestyle include increased energy expenditure, improved physical fitness and the promotion of health. Sedentary behavior is distinct from physical activity and not simply the low end of the PA spectrum; it may be best represented by periods of prolonged sitting.

In the CARDIA Study it is important to measure both types of behaviors since PA and SB have independent health consequences. It is also important to understand the prevalence of different activities, and how this activity spectrum changes as the CARDIA population ages. Further it is important to reliably rank people for overall level of and intensity physical activity, and to determine the impact of types and levels of physical activity and sedentary behavior on the risk of cardiovascular events.

Furthermore, it is important to determine the role of ethnicity on the associations between physical activity or sedentary behavior and CVD, particularly in the hypertension area. Some studies have shown that blacks who performed moderate to vigorous activity have less hypertension than their inactive peers.

The existing questionnaires which initially appeared to be best suited for use in CARDIA were the Minnesota Leisure Time Physical Activity Questionnaire and the Seven Day Physical Activity Recall. The former, which spans twelve months, has been validated against physiologic endpoints, but has not

been shown to be adequately reliable on reapplication, and takes too long to administer. The latter spans only seven days, has considerable accuracy, has shown adequate validity and is suitably brief. However, it too suffers from low repeatability since one week's physical activity is often not representative of general patterns.

In devising a briefer new questionnaire, it was theorized that people could accurately recall or summarize for themselves what and how much activity they do within broad categories. Using an extensive database from the Minnesota Heart Health Program, tabulations were made of activity participation for men and women aged 25-29 years. Based on these tabulations questions were worded for thirteen sets of moderate or vigorous, mostly recreational activities (e.g., vigorous job activities) which might be logically classed together. In this way, details were avoided that are poorly recalled and often irrelevant. A recent evaluation of the CARDIA Physical Activity History (PAH) questionnaire showed that the estimates of physical activity were comparable to those obtained from a more detailed questionnaire that was similar in structure to the CARDIA PAH with the exception that frequency and duration were directly assessed. This same questionnaire has been administered at all exams since baseline.

At the Y30 Exam, most of the original CARDIA PAH is asked, including the series of the thirteen various moderate and vigorous intensity activities. The Y30 Exam also includes a few items from the Baecke self-administered activity questionnaire, but questions excluded at Y25, specifically, comparison to others of the same age and sex and household and childcare activities, are again excluded.

Sedentary behavior has been measured by a proxy question about television watching since the Y5 Exam. This question is again asked at Y30, along with additional questions about time spent sitting in a variety of domains or contexts (e.g., sitting while using the computer for non-work activities or playing video games) that were asked for the first time at Y25 (Form 91).

### **5.13. Genetic Analyses**

CARDIA collected buffy coat for DNA extraction at Y10, Y15, Y20, and Y25. At Y15, cryo-preserved cells were collected for future transformation and immortalization. DNA has been extracted from all Y10 buffy coats and constitutes the primary source of genetic material for the CARDIA studies. This resource has been supplemented with material from the later years' collection. Similarly, at Y30, DNA will be extracted to supplement existing material and complement DNA sets for participants for whom DNA was not previously available in order to obtain as complete a genetic dataset as possible.

### **5.14. Gut Microbiome (Gut Microbiome and CVD Risk Study)**

The ancillary study *A Novel Gut Microbial-Dependent Nutrient Metabolite and Atherosclerosis* (Gut Microbiome and CVD Risk Study) (K01 HL127159; [name], PI) adds a gut microbiome component to the Y30 Exam (Chicago Field Center).

Currently, we lack gut microbiome data from population-based and diverse human cohorts. We address this gap through collection of stool and microbiome analysis in a sample (n=300) of CARDIA participants balanced with respect to age and European-/African-American race (n=75 in each gender-race subgroup). In addition, much microbiome research has come from small-scale clinic-based studies, which lack long-term and in-depth phenotypic data on study participants. By collecting microbiome data from CARDIA, we will be in a unique position to quantify associations between gut microbiome and CVD risk measures accounting for covariates, such as long-term diet and physical activity.

We will use a stool collection kit that we tested in a small sample of adults in North Carolina. Participants were selected from an ongoing cohort study to roughly match the age, gender, and racial

composition of the CARDIA cohort. Of the 20 individuals invited to participants, 17 completed the study. Participants were asked to score the following statement: “The stool collection kit was convenient and easy to use” on a scale of 1 to 5, with 5 reflecting “very much” and 1 indicating “not at all.” The average score was 4.7. Participants were also asked to provide any general feedback that might help us improve the kit. We received no negative comments and one person responded “I’d just like to say that the instructions were easy to understand and I wouldn’t change a thing.” Although study participants may over-report satisfaction, we note that participants reported overall lower satisfaction with a separate pilot activity to collect all urine over a 12 hour period. Of the 17 samples received, one indicated a need for additional emphasis in the instructions, which we have done, to limit the volume of stool collected.

Individuals will be determined ineligible for the CARDIA microbiome study if any of following apply: they have taken antibiotics in the past month; they are currently pregnant; they have had an acute gastrointestinal illness or infections in the past week; they have Inflammatory Bowel Disease, such as Crohn’s Disease or Ulcerative Colitis. Only CARDIA baseline participants will be invited to participate in this study. The study will be complete once 300 participants have completed the study. There will be an equal distribution of African American Males and Females and Caucasian Males and Females.

Stool samples will be collected by study participants in their homes during the CARDIA exam period (June 2015-August 2016). Participants will be recruited into the study at the Year 30 exam by Northwestern Clinic staff. Samples will be analyzed Aug 2016-Jan 2017, bioinformatics performed Feb 2017-June 2017, and statistical analysis conducted July 2017-Jan 2018. We know of no significant risks associated with stool collection, but have given great thought to the development of our stool collection kit to ensure maximal participant safety and convenience. We note in particular that our kit does not require contact with stool beyond what is experienced in daily living or as a part of standard medical tests (e.g., colon cancer screening).

Our kit includes disposable gloves, stool collection tubes (with scoop attached to the lid), and a water soluble bag to line the collection commode; these features ensure that the participant has minimal exposure to their stool. Samples are doubly-enclosed in plastic tubes, sealed into a biohazard bag, and shipped in an insulated cardboard box; these features provide several layers of separation between the samples and participants (as well as other individuals who come in contact with the box). Aside from the stool collection, participants will complete a short survey about variables related to gut microbiome composition, such as antibiotic use and recent gastrointestinal illness.

Our analysis will focus on sequence data from a marker gene (16S rRNA) that has a conserved portion specific to microbiota, as well as variable regions to distinguish phylogenetic groups. We will derive gut composition data from the 16S rRNA sequences. Sequences will be clustered based on a 97% pair-wise sequence similarity, and clusters—operational taxonomic units (OTUs)—will be assigned to bacterial lineages or taxonomies (e.g., genus) through alignment against a reference database. Taxonomic assignments will be used to build a phylogenetic tree, specifying the hierarchical evolutionary relationships among OTUs (e.g., genera within phyla), and providing information about biologically meaningful differences among OTUs (greater evolutionary distance implies greater biologic difference). Due to variability in sampling and sequencing depth, we will normalize the counts by calculating proportions. For each participant, we anticipate that we will have counts and proportions for ~200 OTUs (~100 genera) and a phylogenetic tree.

From these data, we will derive ~15 diversity measures, including measures of alpha-diversity such as richness and evenness, and measures that combine features of diversity (e.g., richness and abundance), including the Shannon Index. We will also derive between-sample (beta-diversity) measures of the compositional similarity/difference between samples, such as Bray-Curtis to measure between-sample dissimilarity based on OTU abundance. Diversity measures will be used to derive summary metrics, such

as Principal Coordinates Analysis (PCoA), which provide information about how data cluster in the community. Summary metrics also reduce dimensional structure for regression analysis. We anticipate that our final set of participant-level gut microbial community variables will include ~200 taxonomic counts (~100 genera), ~5 diversity measures, and the first ~10 clusters from PCoA for a total of ~215 measures.

Several features of OTU data raise challenges for regression analysis, including their high-dimensionality (~100 genera), correlational structure, and distributional attributes (skewed, zero-inflated, and over-dispersed). Some of these challenges can be circumvented by using summary diversity measures or PCoA clusters, which can be included in standard regression models. There are also substantive reasons for modeling diversity measures, as they have been associated with many health outcomes in the literature. We will, therefore rely on diversity measures for our primary analysis. Secondary analysis will include individual regression analysis of distinct taxonomic entities, and penalized regression to include all taxonomic entities in the same model, accounting for their clustered nature. Power will be lowest for the 100 regressions analysis. To account for multiple comparisons (100 distinct regressions), we will use the Benjamini-Hochberg procedure to calculate false discovery rate (FDR). The FDR is less stringent than family-wise error rates (e.g., Bonferroni) at given nominal significance level (alpha), and is preferable for high-dimensional data (here 100 models) as it balances the number of true and false positives. Assuming 10% true positives and a 10% FDR, we will have 80% power to detect differences in continuous variables (e.g., lipids, insulin resistance, blood pressure) of roughly 1 standard deviation comparing participants in the highest and lowest quartiles of genera categories. Differences of this magnitude are clinically meaningful. We will have even greater power for the analysis of gut microbial diversity measures.

#### **5.15. Gut Microbiome (CARDIA Brain MRI Microbiome Study)**

The ancillary study CARDIA Brain MRI Microbiome Study (funded by Intramural Research Program funds, NIA; [name], [name], PIs) adds a gut microbiome component to the Y30 Exam (Birmingham, Minneapolis, and Oakland Field Centers).

**Background.** Exciting new data are emerging showing evidence of gut microbiota and brain interactions that modulate neuronal, hormonal and immunological pathways in the brain. Identifying specific gut microbiota, or clusters of microbiota that may reduce the risk for Alzheimer's disease (AD), would be a major advance in identifying prevention strategies, such as dietary guidance.

[figure not shown]
[figure not shown]
This hypothesis is still in the early stages of testing, particularly in human populations. It is an exciting development, as the current understanding of the gut-brain model brings together bi-directional pathways between the brain and inflammation, stress, systemic metabolism, and the autonomic nervous system. Animal models and clinical studies show possible gut microbe mediation of neuromodulators such as brain-derived neurotrophic factor (BDNF), serotonin,  $\gamma$ -Aminobutyric acid (GABA), and short chain fatty acids. These factors play a role in neurologic diseases, including depression, autism, Parkinson's disease and Alzheimer's disease. Additionally, specific microbes have been shown to modulate the response to different drugs, such as metformin in T2 diabetes. The link between diabetes, small vessel disease, cognitive impairment and the microbiota, is of particular interest.

**Study Objectives.** We propose to test the hypothesis in the longitudinal sub-cohort of 300 participants who participate in the Y30 CARDIA Brain MRI Substudy. CARDIA is an ideal platform to study the gut-brain axis: the cohort is well described and two repeat state-of -the-art 3T MRI scans have been acquired, allowing the investigation of the association of microbiota to MRI indicators of tissue volume

and integrity, perfusion, vascular reactivity and fiber track connectivity in more than 40 regions of interest in the brain.

To ensure comparability with the *A Novel Gut Microbial-Dependent Nutrient Metabolite and Atherosclerosis* (Gut Microbiome and CVD Risk Study), the same protocol [see above] will be used from the kits, distribution of the kits to the participants, shipment of the sample to [name], quality control and analysis. In addition the same short survey about variables related to gut microbiome composition, such as antibiotic use and recent gastrointestinal illness.

Eligibility for the study includes: meets inclusion criteria for the MRI. From this sample, participants will be ineligible for the microbiome study if any of following apply: they have taken antibiotics in the past month; they are currently pregnant; they have had an acute gastrointestinal illness or infections in the past week; they have Inflammatory Bowel Disease, such as Crohn’s Disease or Ulcerative Colitis.

### 5.16. Physical Activity Measurement (CARDIA Activity Study)

The ancillary study *10-Year Changes in Objectively-Measured Physical Activity and Sedentary Behavior in the CARDIA Cohort* (CARDIA Activity Study) (1R56HL 125423-01A1; [name] and [name], PIs) adds accelerometer-based assessment of physical activity and sedentary behavior to the Y30 Exam.

The primary goal of this study is to obtain a second collection of accelerometer data in the CARDIA cohort to evaluate the 10-year changes in objectively-measured PA and SB from early (ages 38-50 years)

to late (ages 48-60 years) midlife in relation to CVD risk while the Y30 core CARDIA exam is in progress. A secondary goal is to conduct a series of three methodological studies obtain preliminary data to support a forthcoming R01 to examine the impact of physical activity change on future disease outcomes and successful aging. Conducted in conjunction with the on-going Y30 CARDIA core exam (June, 2015 to May, 2016), this ancillary study will involve Y30 CARDIA core exam participants (estimated n=3,445) and will include the collection of accelerometer-derived PA and SB (first collected at Y20), providing, for the first time, objective measures of PA and SB change that span early to late midlife. We will also utilize core exam data from Y0 to Y30, including self-reported PA and SB, and measured cardiometabolic risk factors and disease outcomes.

### **CARDIA Activity Study Overview:**

Ancillary study participants will be recruited from each of the four CARDIA clinic sites. Eligibility criteria include: (1) Active CARDIA Study participants and (2) ambulatory without assistance from another person (participants using assistive device are eligible).

For participants, willing to participate, that have not yet attended the Y30 Exam, s/he will be reintroduced to the accelerometer (also assessed using a similar model at the Y20 Exam) and receive instructions on how to properly wear the accelerometer, complete the tracking log, and return the materials using a pre-paid and addressed envelope, in-person, during the Y30 Exam visit. For participants, willing to participate, that have already attended the Y30 Exam, s/he will receive written instructions, the accelerometer, tracking log, and pre-paid and addressed envelope in the mail once the informed consent document has been signed and received at the clinic site. Comparisons of the in-person versus mail-based instruction and distribution of the accelerometer in terms of the differences in percentages of (1) ancillary study refusal and (2) compliance to valid wear time rules represents the first methodological sub-study. The second methodological sub-study will be conducted at the Oakland, CA site, only, and includes a comparison of the ActiGraph 7164 model (used at Y20) and ActiGraph GT3X model (used at Y30) in 100 (n=25 per race/sex group) participants who will simultaneously wear both monitors on their waist for the 7-day observation period. The third methodological sub-study will be conducted at the Birmingham, AL site, only, and includes examining the feasibility of continuous 24-hour sleep-waking time assessment in CARDIA participants. One hundred (n=25 per race/sex group) participants will wear two GT3X ActiGraph monitors, simultaneously, one on the waist for physical activity and sedentary behavior assessment and the other on the wrist for sleep duration and quality assessment. All CARDIA Activity Study participants will receive a telephone call 2-3 days after they started wearing the monitors. During this telephone call, CARDIA Activity Study staff will (1) determine if the participant is wearing the monitor, (2) ask for any remaining questions from the participant, and (3) remind participants to return the monitors after 7 days of data collection. If the accelerometer and related materials are not returned, the participant will receive reminder postcards and telephone calls.

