#### *Procedures to be used:*

Accelerometer (Physical Activity) Measures: We will collect accelerometer data over seven consecutive days using the ActiGraph wGT3X-BT activity monitor (Pensacola, FL), a small, tri-axial piezoelectric accelerometer (4.6 cm x 3.3 cm x 1.5 cm; 19 gm). ActiGraph monitors have been extensively validated in laboratory and free-living conditions. Either in-person or on the telephone, participants will receive an accelerometer package that includes: (1) an initialized accelerometer, (2) detailed written wear instructions, (3) *Activity Monitor Tracking Log*, (4) contact information, and (5) pre-addressed and stamped envelope to return the monitor and record after seven days. In the tracking record, participants will enter the (1) time s/he put the monitor on in the morning, (2) time removed in the evening, (3) time that the monitor was removed and replaced for  $\geq 30$  minutes throughout the day (e.g., bathing or swimming activities), and (4) list of activities done for  $\geq 10$  minutes. Approximately 2-3 days

after the participant is scheduled to begin wearing the monitor, CARDIA Activity Study site staff will call to confirm monitor wear and inquire about any questions or problems.

Each CARDIA site will initialize the monitors to start at 12:00am on Day 1 of data collection using the study participant's unique study ID number. Raw tri-axial data will be sampled at 40 Hz for seven consecutive days. Once the accelerometer and tracking record are returned, data will be downloaded by CARDIA Activity Study site study staff and prepared for processing and analysis. Data will be processed using ActiLife6 software through a digitally matched filter and reintegrated up to 60 second epochs and screened for wear time using the Troiano algorithm (also used at the Y20 Exam). Weekly summary accelerometer estimates will be averaged (across days) for all participants with  $\geq$  four valid days of  $\geq$ 10 hours per day of wear time. The primary estimate, total accelerometer counts, will be calculated using summed counts detected over wear periods, while the secondary estimates, time (i.e., minutes) spent in different intensity levels will be derived using standardized cut-point threshold values. Data checks, including a descriptive analysis of the accelerometer-derived physical activity estimates, will be performed monthly.

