### **6.1. Recruitment**

Retention of CARDIA participants across the four field centers is a primary focus of the Y30 Exam period. Participants should, in general, be scheduled sequentially in order of CARDIA participant ID (PID), i.e. the order in which they were examined at the baseline CARDIA exam.

All participants in the Y0 Exam are eligible for the Y30 Exam. Pregnancy or lactation will not eliminate a participant from the entire exam, but may preclude participation in specific exam components. Pregnancy and/or lactation may extend the window of eligibility for a participant. Similarly, participants who have moved more than 50 miles from their home clinic will be permitted an extended window of eligibility in order to maximize retention of the cohort and minimize the costs of retention. Reimbursements will be allowed within limits, at the discretion of the field center Principal Investigator, to bring back for examination participants who have moved more than 50 miles from their home clinic.

The Y30 Exam recruitment plan is designed to re-examine at least 72% of the surviving CARDIA cohort examined at the Y0 Exam. The plan also provides for extensive monitoring of the process. Each field center is provided scheduling lists designed to achieve the completion of the re-examination within twelve months. Participants who have moved will be monitored so that special recruitment and cost planning can be made in advance. Clinic staff will make every effort to contain the costs associated with bringing moved participants to the clinic during the exam. A description of the initial contact and recruitment process can be found in the Y30 MOO Chapter 2—Guidelines for the Y30 Exam.

Every effort is made to maximize the return rate of the CARDIA cohort. The efforts include performing a partial exam on participants who refuse or are unable to participate in a full exam; and examination at a clinic (field center) other than the participant's home clinic. The CARDIA Study is aiming at as high a rate as possible in order to maximize the long-term potential of the study to chart the natural history and/or evolution of CVD risk factors.

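### CARDIA Activity Study: delivery mode is set by whether the participant had already attended Y30, so the in-person versus mail comparison is confounded with attendance timing and may show, hide or reverse a mode effect

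*Protocol*

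**What the plan says.** The overview in Protocol Section 5.16 gives one rule for each mode. In person: "For participants, willing to participate, that have not yet attended the Y30 Exam, s/he will be reintroduced to the accelerometer" and is taught its use at the exam visit. By mail: "For participants, willing to participate, that have already attended the Y30 Exam, s/he will receive written instructions, the accelerometer, tracking log" and return envelope, sent "in the mail once the informed consent document has been signed and received at the clinic site". The comparison of the two modes follows at once: "Comparisons of the in-person versus mail-based instruction and distribution of the accelerometer in terms of the differences in percentages", with its outcomes listed as "1) ancillary study refusal and (2) compliance to valid wear time rules represents the first methodological sub-study". The procedures part of Section 5.16 defines valid wear as at least "four valid days of" 10 or more hours each.

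Section 5.16 describes no randomisation or matching, and no group at the same stage that receives the other mode. It puts the expected Y30 pool at 3,445 and does not state the split by mode.

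Attendance timing is covered elsewhere. Section 6.1 says "Participants should, in general, be scheduled sequentially in order of CARDIA participant ID (PID"), meaning the order of the baseline exam. It allows an extended window for pregnancy or lactation and for people who live more than 50 miles from their home clinic. Section 7.3 says that a participant who misses an appointment can be returned to the scheduling pool.

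**The concern.** The question is whether the way the device is handed over changes refusal and wear compliance. Under the stated rule, everyone in the mail group attended Y30 before the ancillary study reached them, and everyone in the in-person group attends afterwards. The difference in percentages therefore combines three things: the effect of mode, any difference between earlier and later attendees, and any effect of calendar period or of being approached after the exam instead of at it.

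Refusal may also be a different event in the two groups. Only the mail route is said to require a signed consent form to reach the clinic before the device is sent. The overview does not say how an unreturned form is counted.

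Section 5.16 says the methodological sub-studies are to supply preliminary data for a later grant application. A difference, or the absence of one, that cannot be assigned to mode is weak preliminary data on mode.

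**Working it through.** **Plan's own figure.** There is none. The Protocol gives no sample size, expected rate, significance level or mode split for this sub-study, so nothing can be reproduced. What follows is illustration.

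**From the Protocol.** Total pool 3,445 (Section 5.16). This is an upper bound for the compliance outcome, because people who refuse leave that denominator.

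**Assumed.** Compliance of 85% in early attendees (mail); no true mode effect; later attendees (in person) lower by a gap *g*; total N from 1,000 to 3,445; mail share from 25% to 75%; two-sided 5% test.

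**Formula.** With p₁ = 0.85, p₂ = 0.85 − g, d = p₁ − p₂ and pooled p̄ = (n₁p₁ + n₂p₂)/(n₁ + n₂):

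- SE₀ = √[p̄(1 − p̄)(1/n₁ + 1/n₂)]
- SE₁ = √[p₁(1 − p₁)/n₁ + p₂(1 − p₂)/n₂]
- c = 1.96 × SE₀
- Probability of rejection = 1 − Φ((c − d)/SE₁) + Φ((−c − d)/SE₁)

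**Worked case.** n₁ = 1,722, n₂ = 1,723, g = 0.03. Then p̄ = 0.835, SE₀ = 0.01265, c = 0.0248, SE₁ = 0.01264 and (c − d)/SE₁ = −0.41. The result is Φ(0.41) ≈ 0.66; the other tail is negligible.

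**False mode difference, no true mode effect:**

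| N | Mail share | g = 0 | g = 2 points | g = 3 points | g = 5 points |
|---|---|---|---|---|---|
| 3,445 | 50% | 5% | 36.0% | 66.0% | 97.2% |
| 3,445 | 25% | 5% | 27.3% | 52.4% | 91.5% |
| 2,000 | 50% | 5% | 23.0% | 43.9% | 83.8% |
| 1,000 | 50% | 5% | 13.9% | 24.8% | 54.8% |
| 1,000 | 25% | 5% | 10.8% | 18.3% | 41.4% |

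**True benefit hidden or reversed.** Take mail at 80%, a true in-person benefit of 5 points, N = 3,445 split evenly, and later attendees less compliant by g:

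| g | Expected observed difference (in person − mail) | Rejection |
|---|---|---|
| 0 | +5 points | 97.2% |
| 3 points | +2 points | 32.2% |
| 5 points | 0 | 5.0% |
| 8 points | −3 points | 57.3%, almost all in the wrong direction |

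**The case against.** A reader might infer that the comparison will report a mode difference where none exists. The documents do not support that. A false difference needs early and later attendees to differ in refusal or compliance, and the Protocol gives no such difference, size or direction. With no gap the error rate stays at 5%, and a gap in the other direction would mask a real benefit.

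Timing is also partly administrative. Scheduling follows an order set about 30 years earlier, which weakens the argument for strong selection. The extended windows in Section 6.1 and the rescheduling in Section 7.3 could move some people later, but nothing in the Protocol says that those people comply less.

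A reader might also infer that the sub-study exists to choose a delivery mode for the later grant. Section 5.16 ties the three sub-studies only to preliminary data for a grant on activity change and later outcomes.

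Three further points have force. The Protocol states a difference in percentages and no hypothesis test. Returning a consent form can be seen as part of what mail delivery involves. Covariates and denominators are commonly left to an analysis plan, and that plan is not shown.

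What stands is the assignment rule and the contrast, both fixed in the Protocol. Adjustment in a later plan could reduce the confounding. It could not fully separate mode from timing, because no participants at the same stage receive the other mode.

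**Conclusion.** The point holds in limited form. Mode is determined entirely by prior Y30 attendance, so the stated difference in percentages is confounded with attendance timing and cannot isolate the effect of mode. It may show, hide or reverse one.

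The size is unknown. The illustrative figures (about 66% at a 3-point gap and 97% at 5 points) rest on assumed 85% compliance, an even split and the full 3,445. Across the smaller and unequal groups examined they fall as low as 18% and 41%.

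The scope is narrow: one of three methodological sub-studies under a secondary goal of an ancillary study. The primary accelerometer aim is not shown to be affected. The change is worth making because it is cheap.

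**What to change.** Keep the delivery plan and change the contrast.

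1. Make the main mode estimate the comparison among participants whose Y30 visit fell within a short, pre-stated window (for example 8 weeks) either side of the ancillary start at each centre, adjusted for centre, race and sex. Because scheduling broadly follows ID order, people near that date should be more alike than the full groups.
2. For wear compliance, also adjust for each person's Y20 valid-wear status, or compare change from it, where Y20 data exist. Do not use exam date as a covariate in the full sample: it does not overlap between modes, so the adjustment would be extrapolation. Y20 compliance cannot address refusal.
3. For refusal, use all eligible participants invited as the denominator in both groups, and report unreturned consent forms separately from active refusal.
4. Label the full-sample unadjusted percentages as descriptive and confounded with attendance timing.

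The cost is a change of analysis wording; visit dates and the Y20 accelerometer data are already held. The windowed estimate uses fewer participants and is less precise. Confounding is reduced, not removed, since the two groups are still approached at different stages. Randomising mode among participants at the same stage would separate the two but would alter the delivery plan.
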